***HudsonAlpha Genetic Counselor contacts by site:**

Alabama: [name]

Mississippi: [name]

Louisiana: [name]

SouthSeq Result Return Workflow for Site Genetic Counselors

Variant Review for Cases with WGS findings

1. Receive notification via email that a case has findings and is ready for review in Freedcamp ([SouthSeq-VRC Reports](#))
2. Review case/findings in Freedcamp and provide comments as appropriate (within 24-48 business hours)

Return Results for Cases randomized to Clinical Trial Standard of Care Arm

Preparation

1. Receive message within [Genome Gateway](#) from HA genetic counselor that a case has results ready to be returned (and has been randomized to GC disclosure). Message will include participant ID.
2. Review result report, attached to the message sent in Genome Gateway. Reach out to HA genetic counselor with any questions or concerns.
3. Return of result visit gets scheduled with primary parent contact. Depending on site specific procedures this could be done by the GC or by administrative support. Encourage in-person disclosure if possible.

Disclosure (via phone)

1. Connect recording equipment to phone (phone adapter and recorder).
2. At the scheduled time, call the primary parent contact. Confirm it is a good time to discuss SouthSeq results. Document who (all) is on the phone listening and their relationship to proband.
3. Read script from recording procedure and obtain permission to turn on recorder (see attached “Audio Recording Protocol”).
4. Turn on recorder and state on the recording the participant study ID#.
5. DISCLOSE RESULTS TO FAMILY. Answer questions specific to result disclosure discussion, being careful not to extend discussion into initiating additional care management plans (management examples may still be discussed, just not *initiated* during this encounter).
6. Discuss next steps in SouthSeq for family to expect (see below “Next Steps” list).
7. Find out if they remember their Genome Gateway username/password and website? If not, give it to them. If they don’t remember their password there is a link on the GG website they can click to re-set. (participants.southseq.org)
8. Wrap up conversation. End Recording.
9. Notify site study coordinator disclosure is finished, transfer call to study coordinator if available for post result surveys.

Disclosure (in-person)

1. Make sure recording equipment is available and ready.
2. Have printed copy of result report to give to family.
3. Document who (all) attends disclosure and their relationship to proband.

4. Read script from recording procedure and obtain permission to turn on recorder (see attached “Audio Recording Protocol”).
5. Turn on recorder and state on the recording the participant study ID#.
6. **DISCLOSE RESULTS TO FAMILY.** Answer questions specific to result disclosure discussion, being careful not to extend discussion into initiating additional care management plans (management examples may still be discussed, just not *initiated* during this visit).
7. Discuss next steps in SouthSeq for family to expect (see attached “Next Steps” list).
8. Find out if they remember their Genome Gateway username/password and website? If not, give it to them. If they don’t remember their password there is a link on the GG website they can click to re-set. (participants.southseq.org)
9. Wrap up disclosure. End Recording.
10. Notify site study coordinator disclosure is finished, study coordinator will come into the room to facilitate post result surveys.

Certified Letters (if needed)

1. Certified letter disclosure should be triggered if you cannot reach family after 2 attempts to primary phone plus one attempt at non-household contact.
2. Use certified mail to send result letter and SouthSeq cover letter. Depending on the site, this task could be done by the site coordinator or administrative support.
3. Complete “Result Return” questionnaire at time letter is sent.
4. If contact is made with the family, or if the letter is returned undeliverable, add this information to the “Result Return” survey (in the open text box) and submit it again.
5. Send HudsonAlpha GC message in Gateway to inform of that an update has been made.

Follow-up

1. Complete “Result Return” questionnaire in Genome Gateway (assigned to you by HA genetic counselor).
2. Upload audio recording to computer. Keep copy stored locally on computer. Send file to HA genetic counselor in Genome Gateway. Do NOT upload recording to participant’s account, should be uploaded directly to the HA genetic counselor.
3. (If result return was done by phone) Mail hard copy of result letter to participant. Remember do not include any y additional letters/notes/information.
4. Document results/disclosure clinically at institution. Pass result off to clinical team.

Re-analysis/Amended Reports (if new information leads to change in result)

1. Receive a message from HA GC that an amended report is available, amended report will be uploaded in Genome Gateway.
2. Contact the patient with the new information (likely by phone, but any mode of communication is fine). Utilize audio recorder as described elsewhere.
3. Complete “Amended Result Return” questionnaire in Genome Gateway (assigned to you by HA genetic counselor).
4. Upload audio recording to computer. Keep copy stored locally on computer. Send file to HA genetic counselor in Genome Gateway. Do NOT upload recording under participant’s

account, label the audio file using the SouthSeq study ID instead and upload it to the HA GC only.

5. (If RoR by phone) Mail hard copy of result letter to participant. Remember do not include any additional letters/notes/information.
6. Document results/disclosure clinically at institution. Pass result off to clinical team.

Next Steps (what participants can expect):

- Surveys:
 - Encourage survey completion!
 - There is financial compensation for completion of surveys (\$25/completed survey).
 - There are two brief surveys we will ask you to do on Genome Gateway right away after our conversation.
 - At several points over the next several months there will be new surveys to complete in Genome Gateway (family will receive message/email/text when it is time).
- Result Report:
 - A copy of the result report will be available to view/download in Genome Gateway within next couple of days.
 - A paper copy will also be mailed (if phone disclosure).
 - A copy will also be put in child's medical record.
- Education:
 - Some additional educational information about genetics and the result will be available in Genome Gateway a couple of days post-RoR (family will receive a message/email/text when they are available).
 - Educational materials can be accessed at any time in the future using Genome Gateway.
- Clinical Follow-up:
 - If in-patient still can say that you will discuss result with [relevant doc] and they will make decisions about management. If out-patient, encourage patient to do whatever is needed to get looped into genetics. Avoid doing clinical care during the research result disclosure.
 - Regardless, encourage patients to take copies of results reports to future appointments.

5. State the proband's study ID# clearly on the recording, along with the date and the name of the provider doing the result return.
6. Disclose the results to the participant family. Elicit and answer questions from the family.
7. Once the result disclosure conversation is concluded, end the recording.
8. Give audio recorder back to site coordinator/research nurse.
9. Study Coordinator: Save the audio file to a secure, HIPAA compliant computer or storage drive using the study ID number as the file name, and upload the file within Genome Gateway to the HudsonAlpha genetic counselor assigned to your particular site.* This is done by selecting files on the left side menu, clicking on the person you want to send the file to from the list of people, and then clicking the "add file" button in the top right corner of the screen. This will allow you to select a file from your computer to send.
10. Study Coordinator: Maintain an electronic, backup copy of all audio files on a computer prior to deleting the files from the recording device.
11. HudsonAlpha genetic counselors: review the audio recording for disclosures in the experimental arm of the trial (disclosure by non-genetics provider). This review will occur within a week for negative results, within 72 business hours for positive and uncertain results and any errors will be tracked (minor errors, major errors, safety errors). All errors will be tracked for future aggregate analysis. Only major/safety errors will trigger real-time feedback to the disclosing provider from the genetic counselor. Store all audio files in a centralized, electronic location that is HIPAA compliant, organized by site, randomization arm, and study ID.

***HudsonAlpha Genetic Counselor contacts by site:**

Alabama: [name]

Mississippi: [name]

Louisiana: [name]

SouthSeq Result Return Workflow for Site NICU Providers (non-genetic providers)

Variant Review for Cases with WGS findings

1. Receive notification via email that a case has findings and is ready for review in Freedcamp ([SouthSeq-VRC Reports](#))
2. Review case/findings in Freedcamp and provide comments as appropriate (within 24-48 business hours)

Return Results for Cases randomized to Clinical Trial Experimental Arm

Preparation

1. Your SouthSeq site coordinator will receive a message within [Genome Gateway](#) from the HA genetic counselor that a case has results ready to be returned by a NICU provider. The result report will be uploaded in Genome Gateway to the coordinator.
2. Within NICU team it will be decided which NICU provider will do disclosure. Care should be taken to avoid having provider currently doing care of child do disclosure if possible.
3. Site coordinator will send you a copy of any result reports that you will be responsible for disclosing. This will be sent as a file in Genome Gateway.
4. Review result report. Reach out to HA genetic counselor* (via Genome Gateway) with any questions or concerns.
5. Site coordinator will work with you to schedule return of result visit with primary parent contact. Encourage in-person disclosure if possible.

Disclosure (via phone)

1. Connect recording equipment to phone (phone adapter and recorder).
2. At the scheduled time, call the primary parent contact. Confirm it is a good time to discuss SouthSeq results. Document who (all) is on the phone listening and their relationship to proband.
3. Read script from recording procedure and obtain permission to turn on recorder (see attached “Audio Recording Protocol”).
4. Turn on recorder and state on the recording the participant study ID#.
5. DISCLOSE RESULTS TO FAMILY. Answer questions specific to result disclosure discussion, being careful not to extend discussion into initiating additional care management plans (management examples may still be discussed, just not *initiated* during this encounter).
6. Discuss next steps in SouthSeq for family to expect (see below “Next Steps” list).
7. Find out if they remember their Genome Gateway username/password and website? If not, give it to them. If they don’t remember their password there is a link on the GG website they can click to re-set. (participants.southseq.org)
8. Wrap up conversation. End Recording.
9. Notify site study coordinator disclosure is finished, transfer call to study coordinator if available for post result surveys.

Disclosure (in-person)

1. Make sure recording equipment is available and ready.
2. Document who (all) attends disclosure and their relationship to proband.
3. Read script from recording procedure and obtain permission to turn on recorder (see attached “Audio Recording Protocol”).
4. Turn on recorder and state on the recording the participant study ID#.
5. DISCLOSE RESULTS TO FAMILY. Answer questions specific to result disclosure discussion, being careful not to extend discussion into initiating additional care management plans (management examples may still be discussed, just not *initiated* during this visit).
6. Discuss next steps in SouthSeq for family to expect (see attached “Next Steps” list).
7. Find out if they remember their Genome Gateway username/password and website? If not, give it to them. If they don’t remember their password there is a link on the GG website they can click to re-set. (participants.southseq.org)
8. Wrap up disclosure. End Recording.
9. Notify site study coordinator disclosure is finished, study coordinator to come into the room to facilitate post result surveys.

Follow-up

1. Complete “Result Return” questionnaire in Genome Gateway (assigned to you by HA genetic counselor). If the questionnaire has not yet been assigned with the correct participant ID send a message to the HA genetic counselor to have it assigned.
2. Give audio recorder back to site coordinator for audio file upload to HA
3. Document results/disclosure clinically at institution. Pass result off to clinical team.

Re-analysis/Amended Reports (if new information leads to change in result)

1. Site coordinator will receive a message from HA GC that an amended report is available, with a copy of the amended report.
2. Patient should be contacted with the new information (likely by phone, but any mode of communication is fine). Utilize audio recorder as described above. This re-contact does not have to be done by the same provider who did initial return, however the participant needs to remain the same study arm.
3. Complete “Amended Result Return” questionnaire in Genome Gateway (assigned to you by HA genetic counselor). If the questionnaire has not yet been assigned to you with the correct participant ID send a message to the HA genetic counselor to have it assigned.
4. Give audio recorder back to site coordinator for audio file upload to HA.
5. Document results/disclosure clinically at institution (i.e note encounter in the EMR, upload result letter, etc.). Pass result off to clinical team.

Next Steps (what participants can expect):

- Surveys:
 - Encourage survey completion!
 - There is financial compensation for completion of surveys (\$25/completed survey).
 - There are two brief surveys we will ask you to do on Genome Gateway right away after our conversation.

- At several points over the next several months there will be new surveys to complete in Genome Gateway (family will receive message/email/text when it is time).
- Result Report:
 - A copy of the result report will be available to view/download in Genome Gateway within next couple of days.
 - A paper copy will also be mailed (if phone disclosure).
 - A copy will also be put in child's medical record.
- Education:
 - Some additional educational information about genetics and the result will be available in Genome Gateway a couple of days post-RoR (family will receive a message/email/text when they are available).
 - Educational materials can be accessed at any time in the future using Genome Gateway.
- Clinical Follow-up:
 - If in-patient still can say that you will discuss result with [relevant doc] and they will make decisions about management. If out-patient, encourage patient to do whatever is needed to get looped into genetics/etc. Avoid doing clinical care during the research result disclosure.
 - Encourage patients to take copies of results reports to future appointments.

5. State the proband's study ID# clearly on the recording, along with the date and the name of the provider doing the result return.
6. Disclose the results to the participant family. Elicit and answer questions from the family.
7. Once the result disclosure conversation is concluded, end the recording.
8. Give audio recorder back to site coordinator/research nurse.
9. Study Coordinator: Save the audio file to a secure, HIPAA compliant computer or storage drive using the study ID number as the file name, and upload the file within Genome Gateway to the HudsonAlpha genetic counselor assigned to your particular site.* This is done by selecting files on the left side menu, clicking on the person you want to send the file to from the list of people, and then clicking the "add file" button in the top right corner of the screen. This will allow you to select a file from your computer to send.
10. Study Coordinator: Maintain an electronic, backup copy of all audio files on a computer prior to deleting the files from the recording device.
11. HudsonAlpha genetic counselors: review the audio recording for disclosures in the experimental arm of the trial (disclosure by non-genetics provider). This review will occur within a week for negative results, within 72 business hours for positive and uncertain results and any errors will be tracked (minor errors, major errors, safety errors). All errors will be tracked for future aggregate analysis. Only major/safety errors will trigger real-time feedback to the disclosing provider from the genetic counselor. Store all audio files in a centralized, electronic location that is HIPAA compliant, organized by site, randomization arm, and study ID.

***HudsonAlpha Genetic Counselor contacts by site:**

Alabama: [name]

Mississippi: [name]

Louisiana: [name]

Statistical Analysis Plan

Statistical Analysis: Descriptive statistics were calculated by randomized group. Specifically, for continuous demographic variables, sample means and standard deviations were calculated. For categorical demographic variables, counts and sample proportions were calculated. To test for differences between the randomized groups regarding demographics, two-sample tests were conducted for continuous variables and Chi-square analyses categorical outcomes. Sample means and standard deviations were calculated by randomization group for the primary outcome (GCOS) and secondary outcomes (PUGS, PRU). For all the outcomes, sample means and standard deviations were calculated by genetic testing results (none, variant of unknown significant, pathogenic) within each randomized group. Margin of noninferiority was set per outcome. To test non-inferiority, a one-tailed two-sample test comparing the difference of means, calculated as mean score outcome score of mother's randomized to receive genetic results from genetic counselors minus the mean score outcome score of mother's randomized to receive genetic results from non-genetic providers, to the non-inferiority margin was conducted. The normality assumption was examined using normal-probability plots and histograms. The same testing strategy was used for stratified analyses to determine if non-inferiority could be declared by genetic result types. All tests utilized a Type I error rate of 0.025 and were conducted in SAS 9.4.

Primary outcome

Results of the non-inferiority analysis for the primary outcome of GCOS are first presented by all genetic results combined for each group and then stratified by genetic result type. To conduct a non-inferiority analysis, one must declare a difference between group means, called a non-inferiority margin, such that if the data provides statistically significant evidence that the difference of means is below that margin, then study can declare one group is non-inferior to the other. Non-inferiority designs are by design one-tailed hypothesis tests. Within our study, we sought to demonstrate that the Nongenetic providers are non-inferior to Genetic Counselors. We calculated the difference of means as the Genetic Counselor mean minus the NonGenetic Provider mean and based upon consultation with NIH, a non-inferiority margin of 10 points. We have chosen to conduct the test using a Type I error rate of 0.025. As can be seen in the Results Section, the mean and standard deviation of the Genetic Counselor group is 117.94 ± 13.85 and the mean and standard deviation of the Nongenetic Provider group is 117.19 ± 14.86 . The observed difference between mean is less than 1 point. The test generates a p-value of <0.0001 when using a non-inferiority margin of 10. Using a Type I error rate of 0.025, we can conclude that nongenetic providers are non-inferior to genetic counselors when compared on the GCOS. Because some clinicians may prefer to consider different non-inferiority margins, we have provided a one-tailed 97.5% confidence interval. For the combined genetic results, we are 97.5% confident that the true mean difference is less than 4.83 points. Therefore, the noninferiority margin can be reduced to 4.83 and significance would still be declared. However, if one insists on a margin of non-inferiority less than 4.83 points, our data would not provide sufficient evidence to declare non-inferiority. As can be seen from the stratified analysis, non-inferiority can be declared for the genetic result strata of none and VUS. However, the data does not provide sufficient evidence to declare nongenetic providers noninferior to genetic counselors when the genetic results are pathogenic.

Secondary outcomes

For secondary outcome of PUGS results are first presented by all genetic results combined for each group and then stratified by genetic result type. To conduct a non-inferiority analysis, one must declare a difference between group means, called a non-inferiority margin, such that if the data provides statistically significant evidence that the difference of means is below that margin, then study can declare one group is non-inferior to the other. Non-inferiority designs are by design one-tailed hypothesis tests. As mentioned above we sought to demonstrate that the Nongenetic providers are non-inferior to Genetic

Counselors. We calculated the difference of means as the Genetic Counselor mean minus the NonGenetic Provider mean and based upon consultation with NIH, a non-inferiority margin of 3.5 points. We have chosen to conduct the test using a Type I error rate of 0.025. As can be seen from the table, the mean and standard deviation of the Genetic Counselor group is 29.11 ± 7.31 and the mean and standard deviation of the Nongenetic Provider group is 29.74 ± 5.87 . The observed difference between mean is less than 1 point in favor of the nongenetic providers. The test generates a p-value of <0.0001 when using a non-inferiority margin of 3.5. Using a Type I error rate of 0.025, we can conclude that nongenetic providers are non-inferior to genetic counselors when compared on the PUGS. Because some clinicians may prefer to consider different non-inferiority margins, we have provided a one-tailed 97.5% confidence interval. For the combined genetic results, we are 97.5% confident that the true mean difference is less than 1.22 points. Therefore, the noninferiority margin can be reduced to 1.22 points and significance would still be declared. However, if one insists on a margin of non-inferiority less than 1.22 points, our data would not provide sufficient evidence to declare non-inferiority. As can be seen from the stratified analysis, non-inferiority can be declared for the all genetic result strata of none, VUS, and pathogenic.

The results of the non-inferiority analysis for the secondary outcome of PRU are also first presented by all genetic results combined for each group and then stratified by genetic result type. To conduct a non-inferiority analysis, one must declare a difference between group means, called a non-inferiority margin, such that if the data provides statistically significant evidence that the difference of means is below that margin, then study can declare one group is non-inferior to the other. Non-inferiority designs are by design one-tailed hypothesis tests. Within our study, we seek to demonstrate that the Nongenetic providers are non-inferior to Genetic Counselors. We calculated the difference of means as the Genetic Counselor mean minus the NonGenetic Provider mean and based upon consultation with NIH, a non-inferiority margin of 10 points. We have chosen to conduct the test using a Type I error rate of 0.025. As can be seen in the Results Section, the mean and standard deviation of the Genetic Counselor group is 78.40 ± 20.51 and the mean and standard deviation of the Nongenetic Provider group is 73.93 ± 19.86 . The observed difference between mean is 4.47 points in favor of the genetic providers. The test generates a p-value of 0.0277 when using a non-inferiority margin of 10. Using a Type I error rate of 0.025, we cannot conclude that nongenetic providers are non-inferior to genetic counselors when compared on the PRU. Because some clinicians may prefer to consider different non-inferiority margins, we have provided a one-tailed 97.5% confidence interval. For the combined genetic results, we are 97.5% confident that the true mean difference is less than 10.13 points. Therefore, the noninferiority margin would need to be increased to 10.13 points for significance to be declared. As can be seen from the stratified analysis, non-inferiority can be declared for pathogenic strata.

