Study investigators will audio record the return of results sessions, whether in-person or over the phone, so that GCs at HA can check for minor, major, and high-risk errors in communication of the WGS findings that will be corrected, appropriately. (see appendix 13 for the audio recording process)

(1) Results (ROR) Recordings

Prior to the WGS result disclosure participants will be reminded that the interaction will be recorded using a digital audio recorder, and their GG account username/password will be needed post-ROR for completion of the GCOS and FACToR measures. They will be reminded that the purpose of the recording is to help the study team understand how the results are described and what questions and topics come up during the discussion. Participants will be reminded that the recordings will only be used by the SouthSeq study and no identifiable information will be shared outside of the study team.

Participants are given an opportunity to opt-out of the recording, but their results would have to be delivered by a GC. This can cause a delay if the participant is scheduled to have results delivered by a trained healthcare provider. Participants will not be given a copy of the recording. However, if they self-select to record the session on their own device that is permissible.

The GC or physician conducting the results disclosure will begin by verbally introducing the people attending the return of results session. This introduction/preamble will be scripted (appendix 13), the audio recording is begun and the family ID is stated clearly on the recording, as well as the name of the clinician doing the disclosure.

The parents/caregivers are counseled on the genetic test results, and when the interaction is finished, the recording is stopped. The digital recording file is uploaded in Genome Gateway to the designated HudsonAlpha GC (based on site) by the site study coordinator within 72 hours (3 business days) for positive or VUS results and within 7 business days for negative results. Errors will not be tracked within the GC arm, but only within the trained healthcare provider arm. Below are the HudsonAlpha GCs assigned to each clinical site:

Birmingham, AL (UAB): [name], MS, CGC

Jackson, MS (UMMC): [name], MS, CGC

Baton Rouge, LA (BR): [name], MS, CGC

New Orleans, LA(LSU): [name], MS, CGC

University of Louisville (UL): [name], MS, CGC

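### The published non-inferiority bounds assume no correlation between families told their results by the same clinician; if there is any, 4.83, 1.22 and 10.13 are too narrow to serve as substitute margins

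*Combined protocol and SAP*

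**What the plan says.** Under Statistical Analysis, the SAP compares the two arms by "To test non-inferiority, a one-tailed two-sample test comparing the difference of means" with the margin, and adds that "All tests utilized a Type I error rate of 0.025 and were conducted in SAS 9.4". No clinician term, site term, robust variance or sensitivity analysis appears there or in the outcome sections. Protocol section 3.e.1 randomizes individual families, stratified by site and type of sequencing result; the test uses neither factor.

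For the primary outcome the margin was set "based upon consultation with NIH, a non-inferiority margin of 10 points", and the result is stated as "we are 97.5% confident that the true mean difference is less than 4.83 points". The SAP then tells readers that "the noninferiority margin can be reduced to 4.83 and significance would still be declared". It makes the parallel statement for PUGS at 1.22, and says the PRU margin would have to rise to 10.13.

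Appendix 15 has control-arm results given by the site genetic counselor, by phone or in person. In the experimental arm each site's NICU team chooses a provider for the case. Section 3.e.2 (1) has the recording state the family ID "as well as the name of the clinician doing the disclosure".

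**The concern.** The thing randomized is the person who explains the result. Families who hear results from the same person share that person's skill and style, so their scores may correlate. A two-sample test counts each family as an independent piece of information about the arm. If scores do correlate within clinician, the standard error is too small, its degrees of freedom are too generous, and the one-sided error rate exceeds 0.025.

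This matters here because the SAP goes beyond reporting that the margins of 10 and 3.5 were met. It publishes the bounds as thresholds that a reader with a stricter margin may use, and it presents PRU as a near miss at 10.13. Those statements depend directly on the standard error.

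**Working it through.** **Inputs from the SAP.** GCOS: "standard deviation of the Genetic Counselor group is 117.94 ± 13.85" and "standard deviation of the Nongenetic Provider group is 117.19 ± 14.86", bound 4.83, margin 10. PUGS: 29.11 ± 7.31 against 29.74 ± 5.87, bound 1.22, margin 3.5. PRU: 78.40 ± 20.51 against 73.93 ± 19.86, bound 10.13, margin 10, p = 0.0277. The genetic counselor arm is given first, and the difference d is counselor minus non-genetic provider.

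**Step 1: reproduce the SAP's figures.** The analyzed n is not stated, so I solved bound = d + t(0.975, 2n−2) × √((s₁²+s₂²)/n) for n per arm, assuming equal arms.

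| Outcome | d | SE | Implied n per arm |
|---|---|---|---|
| GCOS | 0.75 | (4.83−0.75)/1.972 = 2.07 | 412.64/2.07² ≈ 96 |
| PUGS | −0.63 | (1.22+0.63)/1.972 = 0.938 | 87.89/0.938² ≈ 100 |
| PRU | 4.47 | (10.13−4.47)/1.972 = 2.870 | 815.08/2.870² ≈ 99 |

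For PRU, t = (10−4.47)/2.870 = 1.927, which gives p = 0.0277, exactly as stated. The three implied sizes agree, so the bounds fit a plain independent-families standard error on about 200 respondents.

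**Step 2: allow for clinician clustering.** The ICC, the number of disclosers and the caseloads are not in the documents. I assume 5–10 counselors, 25–40 NICU providers and an ICC of 0.01–0.10. Each arm's variance s²/n is multiplied by 1 + (m−1) × ICC, where m = n / number of clinicians.

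One case in full (GCOS, ICC 0.05, 5 counselors, 25 providers):
- Counselor arm: m = 96.4/5 = 19.3; variance 1.990 × 1.914 = 3.81.
- Provider arm: m = 96.4/25 = 3.86; variance 2.291 × 1.143 = 2.62.
- SE = √6.43 = 2.535. Keeping about 191 df, the bound is 0.75 + 1.972 × 2.535 = 5.75.
- Satterthwaite df from clinicians minus 1 per arm: 6.43² / (3.81²/4 + 2.62²/24) ≈ 10.6. Then t = 2.212 and the bound is 6.36.

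Over the whole assumed range:

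| Outcome | Stated bound | Variance inflation only | With clinician-level df |
|---|---|---|---|
| GCOS | 4.83 | 4.9–6.5 | 5.1–7.4 |
| PUGS | 1.22 | 1.3–2.2 | 1.4–2.8 |
| PRU | 10.13 | 10.3–12.7 | 10.5–14.1 |

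The last column mixes two effects. With an ICC of zero, 5 counselors and 25 providers, clinician-level df alone already give 5.16, 1.46 and 10.66. The middle column is the cleaner measure of what correlation does.

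**Step 3: how much clustering reverses a pooled verdict?** Before any loss of df, the variance would have to be inflated by (9.25/4.08)² = 5.1 for GCOS and (4.13/1.85)² = 5.0 for PUGS. The GCOS case worked above has 6.43/4.28 = 1.5.

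**Step 4: coverage.** In a simulation with 5 sites, 20 families per arm per site, and one counselor and four NICU providers per site, coverage of the nominal 97.5% bound was about 96.0% at clinician ICC 0.02, 94.2% at 0.05 and 90.7% at 0.10. With a site effect shared by both arms (ICC 0.05) and no clinician effect it was 97.9%, slightly conservative. With both at 0.05 it was 94.6%.

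**The case against.** The strongest reply is that nothing in the documents shows a clinician effect. No ICC is given, so a reader might infer that the bounds are wrong as a matter of fact, and the documents do not support that. This stands: the point is conditional.

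Nor do the documents show that each NICU provider saw many families. Teams are large, the number who disclosed is not stated, and the assumed 25–40 providers for about 100 families means roughly 2.5–4 each. This also stands, but it changes little. With no clustering at all in the NICU arm, 5 counselors and ICC 0.05, variance inflation alone still gives 5.62, 1.69 and 11.37. The counselor arm carries the point. Repeated disclosure by the same counselor is a fair inference from a workflow written around one site counselor, though the number of counselors is not stated either.

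Ignoring the stratification works the other way. That is correct but small: the simulation with both effects still falls short of nominal coverage.

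A reader might also infer that the result-type verdicts are more exposed because the strata are smaller. Stratum sizes and bounds are not in the text, and fewer families per clinician within a stratum would lower the design effect, so this cannot be claimed.

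**Conclusion.** The point holds in conditional form. The published bounds rest on zero within-clinician correlation. If there is any, they are too narrow apart from a small offset from the ignored strata, and the statements that the margin can come down to 4.83 or 1.22 are not supported. The size cannot be derived from the documents; the ranges above rest on assumed ICCs and clinician counts, and on an n back-solved with equal arms.

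A reader might infer that the primary conclusion is unsafe. It is not within this range: the largest bounds, 7.4 for GCOS and 2.8 for PUGS, stay inside 10 and 3.5. A reversal needs more extreme assumptions. At ICC 0.20 with only 5 counselors and clinician-level df, PUGS passes 3.5 (3.71 with 40 NICU providers, 4.15 with 5), and GCOS passes 10 (11.05) only if there are also just 5 NICU providers. PRU already fails; what changes there is how near a miss it appears.

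**What to change.** Fit a linear mixed model for each outcome with arm, site and result type as fixed effects and disclosing clinician as a random effect, using Satterthwaite or Kenward-Roger degrees of freedom. Report its bounds for GCOS, PUGS and PRU beside the two-sample bounds, and base any statement about how far the margin can be reduced on the wider of the two. Report, by arm, the number of disclosing clinicians, families per clinician and the estimated ICC.

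The cost is analysis time. The clinician is named on the recordings, and disclosers in both arms complete a Result Return questionnaire, which should help identify the discloser where a control family declined recording. The downsides are that the bounds may widen, that the clinician variance will be imprecise with few counselors, and that with about one counselor per site the counselor and site effects are hard to separate in the control arm. If the estimated ICC is near zero, that supports the published bounds, subject to that imprecision.
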